### Survey - CSRI

Service utilization data collected through the CSRI will be used to map resource usage patterns for individual subjects and to determine associations between resource usage and socioeconomic status. Applicable events in medical history will be summarised using ICD-10 classification.

### Health care costs

Direct medical costs associated to COM-related health care utilisation will be calculated for each subject using standard cost/unit in each participating country. Costs for individual contacts will be assigned with a view to identifying COM related health care cost factors for individual subjects and for groups of interventions, where feasible. All comparisons will be presented as aggregated data without the possibility of identifying data from individual subjects.

Estimation of costs will be based on primary outcomes that will be allocated a unit cost. The base case analysis will employ standard unit costs from all the included countries on the pooled data on utilisation and adjusted to the cost year 2022 and converted into Euros using the World Bank conversion factor for purchasing power parity. Health care costs in the population will be based on the health care consumption from primary tympanoplasty to enrolment (analysed in patient-years) and assumptions on when a state of stability is reached, which will be determined using data collected as part of this investigation itself.

### Patient reported outcome

Attribute levels and scores will be calculated for individual subscales and general scores for each subject. If possible, data will also be grouped by intervention type and differences in scores between these groups will be analysed. Change in score will be assessed using the Wilcoxon rank sum test and sub-group analyses by age and gender may be performed, if feasible.

### Validation of COMOT-15 in French and Spanish

The validated German version of the COMOT-15 that has been translated, back translated and linguistically validated will be used to validate the instruments reliability in French and Spanish. The instrument will be administered according to the original procedure and criterion validity will be assessed by comparing COMOT-15 scores with PTA4. COMOT-15 properties, including internal consistency will be assessed using Cronbach's alpha, where a value of >0.7 is indicative of acceptable reliability for clinical purposes.

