### 7.2.1 Inclusion Criteria

Subjects must meet all of the inclusion criteria described below to be eligible for this clinical investigation.

1. Adult subjects, 18 years or older.
2. Subjects with conductive or mixed hearing loss.
3. Subjects with historically documented diagnosis of Chronic Otitis Media (COM) with or without cholesteatoma in the operated ear.
4. Subjects who have undergone primary tympanoplasty type I-V to improve hearing between 2010-2016.
5. Subjects with a PTA4 air-bone gap  $\geq 30$  dB OR PTA4 air-bone gap between 25-30 dB with an air conduction threshold PTA4  $\geq 40$  dB HL within 12 months after primary tympanoplasty in the operated ear.
6. Subjects who have been recommended by their health care professional to try a hearing aid to improve hearing in the operated ear.
7. Pre-op audiogram, maximum 1 year prior to the primary tympanoplasty, and post-op audiogram for the primary tympanoplasty are available.
8. Aided audiogram, unaided if no hearing device is used, available between 2018 and the point of enrolment.
9. Subjects are fluent in the language used for study questionnaires: German, French, Spanish.
10. Subjects are willing and able to provide written informed consent.
11. Medical Record data is available throughout the defined data search period, from primary tympanoplasty to point of enrolment.

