#### Chronic Otitis Media Outcome Test-15 (COMOT-15) and validation in French and Spanish

The subjects will be asked to complete a Chronic Otitis Media Outcome Test-15 (37).

COMOT-15 is 15-item questionnaire that is a reliable and sensitive instrument for measurement of HR-QoL of subjects with COM.

The instrument consists of three subscales: ear symptoms (questions 1-6), hearing function (questions 7-9), and mental health (questions 10-13), which form the overall score (questions 1-13). In addition, one question on the general evaluation of the impact of COM on QoL (question 14) and one question to indicate the frequency of doctor visits in the last six months as a result of COM (question 15) are asked. The total score and the sub-scores are transformed to a 0-100 scale by dividing the sum of the raw scores of the items by the sum of spans of the items followed by multiplying by 100. Overall scores and sub-scores will be calculated for subjects based on this methodology, and compared between interventions, if feasible. COMOT-15 is validated in German and will be used in its original version at German-speaking clinics. For non-German speaking clinics, the COMOT-15 has been cross-translated and linguistically validated in Spanish and French by a certified translation agency (Software and Documentation Localization PLC) using published methodology (38). As the COMOT-15 is a COM-specific questionnaire that has already demonstrated reliability in additional languages, validation of the instrument in French and Spanish will require that

the questionnaire is completed by a minimum of 30 subjects per language, based on the accepted subject to item ratio of at least 2 (29). These subjects must have an accompanying audiogram (PTA4 at minimum) collected within 12 months of questionnaire completeness and completed the SSQ and HUI3 questionnaire as part of the investigation. Aided audiograms should be collected if the subject is using a hearing device. The widely accepted Cronbach's alpha value of 0.7 will be used as a cut-off to measure consistency.

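### The reliability verdict on the French and Spanish COMOT-15 compares a bare Cronbach's alpha with 0.7, on a set that is not clearly defined and may be as small as 30 per language

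*Combined protocol and SAP*

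**What the plan says.** Validation of the COMOT-15 in French and Spanish is the fifth secondary objective (Section 6.2).

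- **Criterion.** Section 9.7 assesses internal consistency by Cronbach's alpha, "where a value of >0.7 is indicative of acceptable reliability for clinical purposes". Section 7.3.2.1 is firmer: "The widely accepted Cronbach's alpha value of 0.7 will be used as a cut-off to measure consistency". Neither section gives a confidence interval, a rule for the lower limit or a precision target.
- **Number.** Section 7.3.2.1 requires that "the questionnaire is completed by a minimum of 30 subjects per language, based on the accepted subject to item ratio of at least 2". Section 7.2.3 repeats 30 as a minimum with complete data.
- **Who counts.** Section 7.3.2.1 continues: "These subjects must have an accompanying audiogram (PTA4 at minimum) collected within 12 months of questionnaire completeness". The same subjects must also have completed the SSQ and HUI3. Entry to the study is wider. Inclusion criterion 8 asks for: "Aided audiogram, unaided if no hearing device is used, available between 2018 and the point of enrolment".
- **Analysis set.** The validation paragraph in Section 9.7 names no set for alpha. Section 9.1 places every analysis on the full data set, and Section 9.5 defines the full analysis set as everyone enrolled.
- **Scores.** Section 7.3.2.1 defines three subscales of 6, 3 and 4 items, which together make a 13-item overall score. Neither section says whether the 0.7 rule applies to the overall score, the subscales or both.

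**The concern.** Three features combine.

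1. A point estimate compared with a cut-off carries no statement of its own uncertainty. The minimum of 30 comes from a subject-to-item ratio, which says nothing about how precisely alpha will be known.
2. The audiogram condition makes sense for criterion validity, where COMOT-15 scores are compared with PTA4. It has no bearing on alpha, which is calculated from the item responses alone. Section 25 explains that version 4.0 widened criterion 8 to admit subjects with no follow-up audiogram in the 12 months before enrolment. Some completers can therefore be expected to fall outside the 12-month condition. Under Section 7.3.2.1 they could be left out of alpha; under Sections 9.1 and 9.5 they would be included. Two analysts could follow the plan and report different values.
3. The subscale scores will be reported and, where feasible, compared between interventions. Short subscales have the least precise alpha, and the plan does not say whether they are tested.

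At stake is the claim that the two translations are reliable. It could rest on an estimate compatible with clearly inadequate consistency, or be withheld from an adequate scale.

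**Working it through.** **Inputs from the plan.** Minimum n = 30 per language; 15 items in all; k = 13 in the overall score; subscales of k = 6, 3 and 4 (all Section 7.3.2.1). Cut-off 0.7 (Sections 7.3.2.1 and 9.7). Total 200 subjects at 6 to 9 sites in three countries, with even numbers per site as the aim and reallocation allowed (Section 7.1).

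**The plan's own figure.** 2 subjects per item × 15 items = 30, so the minimum reproduces. The 13 scored items alone would give 2 × 13 = 26.

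**Precision of alpha.** Feldt's result is that (1 − α)/(1 − α̂) follows an F distribution with n − 1 and (n − 1)(k − 1) degrees of freedom. The 95% limits are therefore 1 − (1 − α̂) × F, taken at the 97.5% point of F for the lower limit and the 2.5% point for the upper.

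For n = 30 and k = 13 the degrees of freedom are 29 and 348, and the two F points are 1.619 and 0.545. At an observed alpha of 0.70:

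- lower limit 1 − 0.30 × 1.619 = 0.51
- upper limit 1 − 0.30 × 0.545 = 0.84

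For the 3-item hearing subscale the same steps give 0.45 to 0.85.

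**Behaviour of the rule.** An observed alpha above 0.7 is the event F > (1 − α)/0.30. With n = 30 and k = 13:

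- true alpha 0.60: P(F > 1.333) = 0.121
- true alpha 0.65: P(F > 1.167) = 0.257
- true alpha 0.75: P(F > 0.833) = 0.716, so the scale fails with probability 0.284

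At true alpha 0.60 the pass rate is 13.7% for the 6-item subscale, 15.5% for the 4-item and 17.4% for the 3-item. Simulation with 20,000 replicates at true alpha 0.60 and n = 30 gave 11.8% for 13 items and 17.3% for 3 items, in line with the formula.

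**How many completers there might be.** The plan gives no number per country or language beyond the minimum. Assuming even enrolment per site and full return of questionnaires, a language with 2 of 9 sites has 200 × 2/9 = 44 subjects, one with 3 of 9 or 2 of 6 has 67, and one with 4 of 9 has 89. For the 13-item score:

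| n | 95% CI at observed 0.70 | Pass if true alpha 0.60 | Fail if true alpha 0.75 |
|---|---|---|---|
| 30 | 0.51–0.84 | 12% | 28% |
| 44 | 0.55–0.82 | 8% | 23% |
| 67 | 0.58–0.80 | 4% | 18% |
| 89 | 0.60–0.78 | 2.5% | 14% |

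More subjects help, but even at 89 an observed 0.70 is compatible with a true value of 0.60. For the 95% lower limit to reach 0.7, the observed 13-item alpha must be about 0.815 at n = 30 and 0.784 at n = 67.

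**The case against.** The strongest reply is that the plan does not confine alpha to the audiogram-qualified subjects. The condition in Section 7.3.2.1 is attached to the minimum of 30, and that validation includes the PTA4 comparison, which explains why it is there. Sections 9.1 and 9.5 point to everyone enrolled. This stands. A reader might infer that the plan throws away usable completers, but the documents show only that the set is undefined.

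A reader might also infer that about twice as many completers are available as the plan would use. That does not follow. Thirty is a floor, not an expected number. The figure of 67 needs an equal split by country, whereas the plan aims for evenness by site. Subjects with a follow-up audiogram due in the recruitment period complete the questionnaires at that appointment, so they would normally meet the 12-month condition. The share outside it is not given and could be near zero. The rows of the table show precision at different sizes; they do not measure a loss caused by the audiogram condition.

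Nor is the rule a coin toss because n is 30. If true alpha is 0.70, a point-estimate rule passes roughly half the time at any size (47% at n = 30, 48% at n = 67). What 30 subjects do is widen the band around 0.7 in which the verdict is unreliable.

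Finally, the study is descriptive, states no hypotheses, and claims no error rate for this validation. That bears on how serious the point is. It does not remove it, because Section 7.3.2.1 does call 0.7 a cut-off and the outcome will be read as a verdict on the two translations.

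**Conclusion.** The point holds as a minor one. Reliability is judged by a point estimate alone, with a floor of 30 per language that carries no precision argument. At that floor the 95% interval at an observed 0.70 is 0.51 to 0.84 for the overall score and 0.45 to 0.85 for the hearing subscale. Wrong verdicts occur about 12% of the time at true alpha 0.60 (17% for the 3-item subscale) and about 28% at true alpha 0.75. These figures rest on Feldt's distributional assumptions and on n being exactly 30; a larger achieved n improves them.

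The analysis set for alpha and the scores to which 0.7 applies are both unclear. The documents do not support a stated number of discarded subjects, and the range of 44 to 89 completers per language depends on assumed site splits before non-return. The primary endpoint is not affected.

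**What to change.** In Section 9.7, and in Section 7.3.2.1 to match:

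- Compute alpha separately for French and Spanish, on every subject with a complete COMOT-15.
- Report it for items 1 to 13 and for each of the three subscales, with a 95% interval by Feldt's method.
- Apply the 12-month audiogram condition to the PTA4 comparison only.
- Keep 0.7 as the reference and word the conclusion by the interval. For example, separate a lower limit above 0.7 from an estimate above 0.7 whose interval extends below it.

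The interval is the essential part, since a larger n alone does not settle results near the threshold. The cost is a change of wording, with no extra subjects, data or visits. The one downside is that the stated conclusion may be more cautious than a bare pass.

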## 9.8 Exploratory Endpoint Analyses

### Middle Ear Risk Index factors

The Middle Ear Risk Index (MERI) will be used to guide the extraction of middle ear status variables from the medical records (40). If available, pre-operative factors collected from the medical records will be used to populate the MERI, generating a risk score for individual subjects by summing the corresponding risk factor scores defined within each section of the index. Subjects will be stratified into a low-medium-risk group (MERI: 0–7) and a high-risk group (MERI: 8–15). The relationship between pre-operative factors corresponding to those contained in the MERI on the success rate of tympanoplasty, based on post-operative ABG, will be investigated using a binary logistic regression model. The Spearman correlation coefficient will be used to determine relationships between pre-operative factors and their influence on post-operative outcomes.

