#### 4.1.2 Hearing outcomes

Studies use several assessment methodologies and the overall clinical benefits of individual treatments in restoring hearing have not been systematically assessed, particularly not over the long-term. It is frequently reported that surgeries result in non-discharging ears, but it is also obvious that there is a subset of patients who do not show satisfactory improvements in hearing performance following surgery and that post-operative hearing outcomes in some patients actually deteriorate (21, 22). The condition of the ossicular chain is of key importance to hearing outcomes. A retrospective study of 213 patients demonstrated that an intact ossicular chain is significantly associated with improved long-term hearing outcomes after tympanoplasty for perforated COM (23). Patients with a compromised ossicular chain are likely to benefit from bone conduction hearing aids following mastoidectomy (24). It is crucial to understand how surgical intervention could affect hearing since there is extensive evidence of mild to moderate CHL in COM patients before surgery (25). These patients are also predisposed to developing MHL as the disease progresses (26). Studies also stress the need for performing audiology to assess the patients' type and degree of hearing loss prior to treatment intervention since this is not routinely completed (27). Finally, even when audiology is performed the methodology varies, making an accurate comparison difficult.

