### 9.2.3 Exploratory Endpoints

1. Middle Ear Risk Index factors (preoperative status, intraoperative findings) and surgical outcomes, if available.
2. Data on employment status collected in the CSRI survey used to determine the number of lost working hours as a result of COM.

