### **Preoperative Status – if available**

Side of operation

Symptoms

Middle Ear status

Contralateral ear

Presence of extracranial complications

Presence of intracranial complications

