### **Intraoperative Findings – if available**

Cholesteatoma

Extent of cholesteatoma

Type of cholesteatoma

Retraction pocket

Retraction pocket location

Mobility of retraction pocket

Perforation size

Perforation location

Ossicular Erosion

Ossicle eroded  
Ossicle fixed  
Middle ear mucosa  
Active discharge  
Presence of Middle Ear Effusion  
Facial Nerve  
Fistula  
Fistula with labyrinth disturbance  
Canal Wall destruction  
Tegmen destruction that require repair  
Brain herniation into mastoid cavity

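### Section 9.8 scores the MERI from pre-operative factors while the endpoint also includes intraoperative findings, and no rule covers incomplete totals judged against the full-scale cut-offs

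*Combined protocol and SAP*

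**What the plan says.** - **Scoring rule, section 9.8 (Middle Ear Risk Index factors).** Where available, "pre-operative factors collected from the medical records will be used to populate the MERI, generating a risk score for individual subjects by summing" the item scores from every section of the index. The same pre-operative label is used for the predictors in the logistic regression and in the Spearman analysis.
- **Cut-offs, same section.** "Subjects will be stratified into a low-medium-risk group (MERI: 0–7) and a high-risk group (MERI: 8–15").
- **Endpoint, section 9.2.3, repeated in the synopsis.** "Middle Ear Risk Index factors (preoperative status, intraoperative findings) and surgical outcomes, if available".
- **Data collected, Appendix 1.** One block is headed "Preoperative Status – if available". It holds side of operation, symptoms, middle ear status, contralateral ear and complications. A separate block for intraoperative findings, with the same availability condition, holds cholesteatoma, perforation, middle ear mucosa, active discharge and "Ossicular Erosion", among others.
- **Analysis set, sections 9.1 and 9.5.** All analyses use the full data set, which is every enrolled subject. No section gives a minimum number of MERI items, a prorating rule or an exclusion rule for incomplete scores.

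**The concern.** The endpoint draws the MERI from two sources and the scoring rule names one. A programmer working from 9.8 alone would take the pre-operative block, add up what is there, and compare the sum with thresholds built for the whole index. Several middle ear findings appear by name only in the intraoperative block. Among them is the state of the ossicles, of which section 4.1.2 says: "The condition of the ossicular chain is of key importance to hearing outcomes".

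The second gap remains even if both blocks are meant. All of these data are optional, and under a plain sum an unrecorded item can pass silently as no risk. Risk class could then partly reflect how complete a site's surgical records are. What is at stake is the risk score and the two-group split, which serve the exploratory objective of classifying middle ear severity. No primary or secondary endpoint depends on them.

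**Working it through.** The plan gives no figure for how many subjects will fall in each risk group, so there is nothing to reproduce. The check is the arithmetic of an incomplete sum.

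**Inputs from section 9.8:** a plain sum, total range 0 to 15, high risk at 8 or more.

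**Assumptions not in the documents:** no item has a negative score, and an omitted or missing item adds zero. Item weights are not given, so the points carried by the omitted items are varied.

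**Step 1: ceiling.** Let k be the points available on the items left out. The highest reachable total is 15 − k.

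**Step 2: who can cross the cut.** A subject with full score T loses d points, with d between 0 and k. The recorded total is T − d. A high-risk subject falls into the lower group if T − d ≤ 7, that is if d ≥ T − 7. Since d is at most k, the full scores that can fall are 8 to 7 + k. Since d is never negative, nobody can move up.

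| k (assumed) | Ceiling, 15 − k | Full scores that can fall to 7 or below |
|---|---|---|
| 1 | 14 | 8 |
| 3 | 12 | 8–10 |
| 4 | 11 | 8–11 |
| 6 | 9 | 8–13 |
| 8 | 7 | 8–15, so all of them |

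At k = 6 only a recorded 8 or 9 out of 9 reaches the high-risk group. At k = 8 nobody can.

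**Step 3: illustration of scattered missingness.** Suppose full scores were uniform on 0 to 15 and each point were captured independently with probability c. The share of truly high-risk subjects moved down is 1 − (1/8) × Σ P(Bin(s, c) ≥ 8), summed over s = 8 to 15.

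| c (assumed) | Share moved down |
|---|---|
| 0.9 | 11% |
| 0.8 | 25% |
| 0.7 | 42% |
| 0.6 | 62% |
| 0.5 | 80% |

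These percentages show how sensitive a fixed cut is to missing points. They are not estimates for this study, since neither the score distribution nor c comes from the documents.

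**Step 4: the same check with a completeness rule.** If a total is formed only when every item is recorded, then d = 0 for every scored subject and the shift from this cause is zero.

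**The case against.** The strongest reply is that the pre-operative wording is a loose label for all baseline index items, including those confirmed at surgery. Section 9.8 sums over every section of the index, contrasts these factors with post-operative outcomes, and applies cut-offs that span the whole scale. The intraoperative items are also collected. That reading is possible. Against it, the endpoint and Appendix 1 both treat pre-operative status and intraoperative findings as separate things, and 9.8 uses the pre-operative label three times without mentioning the other block. The two sections need to be reconciled either way.

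The availability condition could also mean that a score is produced only where its inputs exist. If so, no downward shift arises. The plan does not say this, and its general statements about the full data set do not point that way.

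A reader might infer several stronger things that the documents do not support:

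- **That scores are biased low as a matter of fact.** This depends on absent items counting as zero, which is not stated.
- **That the ossicular findings are certainly left out of the score.** The index items and weights are not listed, and the pre-operative middle ear status field and the demographic risk factors field are undefined and might overlap with them.
- **That no subject could be high risk.** This follows only at an assumed k of 8.
- **That the exploratory objective fails.** The logistic and Spearman analyses are described on the factors, not on the two risk groups, and they can proceed without the split.

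**Conclusion.** The point holds in a limited, conditional form. Section 9.8 conflicts with section 9.2.3 and the synopsis on which findings feed the MERI, and no rule covers an incomplete total. If omitted or missing items add zero, the error has one direction: totals are too low, and any misclassification is from high risk to low-medium risk. Its extent follows the 15 − k ceiling and the 8 to 7 + k range, but the number of subjects affected cannot be derived, because item weights and missingness are not in the documents. Read literally, the factor-level models would also leave out the intraoperative predictors. Severity is minor: the effect is confined to one exploratory endpoint in a study with no formal hypotheses.

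**What to change.** In section 9.8:

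1. State that the MERI is populated from pre-operative status and intraoperative findings, in line with 9.2.3 and the synopsis.
2. List each index item with its Appendix 1 source field. This also shows whether every item has a field, which cannot be confirmed from the documents as they stand.
3. Use the same set of factors in the logistic and Spearman analyses.
4. Calculate the total and risk group only when all items are recorded.
5. For other subjects, report the lowest possible total (the recorded sum S) and the highest (S plus the points available on that subject's missing items, k). Assign a group only if both lie on the same side of the 7/8 cut: high risk if S ≥ 8, low-medium if S + k ≤ 7. Otherwise label the subject not classifiable. With k = 3, for example, S of 5, 6 or 7 is not classifiable.
6. Report the number not classifiable by site.

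The cost is a wording change, since both data blocks are already collected. The downside is fewer subjects with a risk group. Those with complete records may also differ from the rest, which the bounds and the site counts would help to show.

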## 6.3 Exploratory Objectives

1. Develop scoring system to classify severity of middle ear status and relate to surgical outcome.
2. Estimation of productivity losses.

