### 7.1.1 Design Rationale

This study is designed to collect information regarding health care interventions that follow a primary tympanoplasty with residual hearing loss among adult subjects with diagnosis of COM, with or without cholesteatoma. A multicentre set-up is necessary to accurately capture the standard of care as this can vary at each site, as determined by treatment practice surveys at potential sites and it is important that we capture outcomes on all potential interventions that may be offered as part of standard care. The rationale to collect information from subjects who underwent a primary tympanoplasty procedure between 2010-2016 is to increase the likelihood of availability of electronic medical records data as these systems have only typically been introduced in recent years. This inclusion time frame is also important to capture the current standard of care rather than outcomes from obsolete procedures and to find enough subjects that have at least five years follow-up data so that we may capture patients who have reached a steady state. Subjects with single-sided deafness are not eligible for the study as COM with or without cholesteatoma leads to mainly conductive or mixed hearing loss. Paediatric subjects are excluded from the study as tympanoplasties are delayed until adulthood in some clinics.

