## 7.2.5 Recruitment and Study Duration

The following subject status definitions apply:

- Enrolled: A subject that has signed the Informed Consent Form (ICF) for the study.
- Screen Fail: An Enrolled subject that has been determined to not meet one or more eligibility criteria.
- Participated: Subjects who have met eligibility criteria and have started on protocol defined events.
- Withdrawn: An Enrolled subject who withdrew or was withdrawn by the Investigator or Sponsor before the expected End of Study.
- Completed: Enrolled subjects who complete the required tasks and schedule.

The recruitment period for the clinical investigation is estimated to be approximately 12 months from the time of first subject enrolled to the last subject.

Recruitment of subjects shall be performed in a back-chronological order from the primary tympanoplasty surgery. Recruitment shall start with the last subject that has undergone this procedure in the year 2016 and chronologically working backwards until recruitment targets are met. This process will avoid any recruitment bias.

The expected duration of each subject's participation in the clinical investigation is the time it takes for the subject to complete and return the ICF, questionnaires and survey. Time for completing the questionnaires is estimated to 30-40 minutes.

Clinical Investigation completion is defined as the recording and completion of the last medical record search for the last enrolled subject in the electronic Case Report Forms (eCRF).

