## 9.5 Analysis Populations

Full analysis set consists of all subjects enrolled in the study.

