### Audiogram (BAS) – For Pre- and post-primary tympanoplasty and latest available audiogram only for the operated ear

Date

Presentation Mode (AC, BC)

Aided or Unaided

Masked/Unmasked

Device details

250 Hz - 8K Hz

Result Qualifier

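### Section 9.8 models tympanoplasty success from post-operative ABG in a sample that criterion 5 restricts to ears with a post-operative ABG of at least 25 dB, and naming a cut-off would not cure this

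*Combined protocol and SAP*

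**What the plan says.** Exploratory objective 1 (Section 6.3) is: "Develop scoring system to classify severity of middle ear status and relate to surgical outcome". Section 9.8 sums MERI factors into a risk score, splits subjects into MERI 0-7 and 8-15, and states that the relationship of the pre-operative factors "on the success rate of tympanoplasty, based on post-operative ABG, will be investigated using a binary logistic regression model". Spearman correlations with post-operative outcomes are also planned. Section 9.8 does not say which ABG counts as success or on which audiogram it is read.

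Criterion 5 (Section 7.2.1 and synopsis) requires, within 12 months after the primary tympanoplasty in the operated ear, a PTA4 ABG of at least 30 dB "OR PTA4 air-bone gap between 25-30 dB with an air conduction threshold PTA4" of at least 40 dB HL. All inclusion criteria must be met, and Section 7.1.1 describes the target as tympanoplasty with residual hearing loss.

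Appendix 1 collects audiograms "For Pre- and post-primary tympanoplasty and latest available audiogram only for the operated ear". Criterion 7 requires a post-operative audiogram but sets no window for it. Section 9.5 states: "Full analysis set consists of all subjects enrolled in the study".

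**The concern.** Criterion 5 and the Section 9.8 outcome use the same measurement, on the same ear, after the same operation. An ear that did well on ABG is not eligible, and no cohort of successful ears is described. A regression of success on risk factors needs both results, sampled without regard to the result. Here the sample is cut off on the outcome itself.

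At stake is what may be concluded about MERI. A weak or absent association could be read as evidence that MERI does not predict hearing success after tympanoplasty, when the design would tend to weaken that association in any case. Because the cut-off and audiogram are open, they could also be settled after the data are seen.

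**Working it through.** **The plan's own figure.** None is given for this analysis. The only sample-size figure (Section 9.4, Table 1) concerns seeing a rare intervention at least once. For p = 0.02 and n = 200, the expected number is 200 × 0.02 = 4 and the probability is 1 − 0.98^200 = 0.982, which matches the table. Section 9.4 says the study does not test strengths of association, so this figure does not bear on the MERI model.

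**Step 1: cut-offs on the qualifying audiogram.** Let success mean ABG below c. Eligible ears have ABG ≥30 dB, or 25-30 dB with AC ≥40 dB HL, and BC = AC − ABG.

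| Cut-off c | Successes among eligible ears |
|---|---|
| c ≤ 25 dB | None. The lowest eligible ABG is 25 dB, so a logistic model has no finite odds ratio. |
| 25 < c ≤ 30 dB | All from the second limb: AC ≥40, so BC > 40 − 30 = 10 dB HL. An ear with ABG ≥30 dB has no AC condition, so a failure can have AC as low as 30 dB HL (at BC 0). |
| c > 30 dB | Both limbs, but the model only separates smaller from larger residual gaps. |

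Listing all AC/BC pairs on a 1.25 dB grid confirms this: 0 eligible success cells at c = 15, 20 and 25, and at c = 27.5 and 30 only cells from the second limb. These are bounds, not prevalences. The only success benchmark in the documents, closure within 20 dB (Section 4.2.2), is background that Section 9.8 does not adopt. It would fall in the first row.

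**Step 2: other audiograms.** Because criterion 7 sets no window, the recorded post-operative audiogram need not be the one that met criterion 5. The latest audiogram (2018 to enrolment) is a further candidate. Its interval from surgery can run from about 1.0 year (31 Dec 2016 to 1 Jan 2018) to about 13.2 years (1 Jan 2010 to 31 Mar 2023). The upper figure is a corner case: recruitment works backwards from 2016 and its dates are estimates. Either audiogram could give both classes, but entry still depended on a poor early ABG.

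**Step 3: illustration of range restriction.** Only one input is from the documents: 30.0% of ears with ABG ≥20 dB (Section 4.2.2). The rest are assumptions: normal ABG, half the ears high-risk, SD 10 dB, high-risk shift 5 dB, AC condition ignored. The group means are then about 12.1 and 17.1 dB. Check: P(ABG ≥20) = (0.215 + 0.386)/2 = 0.30.

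- All operated ears, c = 30: P(success) is 0.963 (low-medium risk) and 0.902 (high risk). OR = (0.9015/0.0985)/(0.9633/0.0367) = 0.35.
- Eligible ears (ABG ≥25): P(success) is (0.9633 − 0.9015)/0.0985 = 0.627 and (0.9015 − 0.7852)/0.2148 = 0.541. OR = (0.541/0.459)/(0.627/0.373) = 0.70.
- Over SD 8-15 and shift 3-8 dB, the OR is 0.10-0.68 in all ears and 0.47-0.88 in eligible ears.
- Latest audiogram with c = 20, SD 10, shift 5 and correlation 0.3-0.9 with the early ABG: about 50% down to 6% successes. OR is 0.52-0.68 in eligible ears against about 0.43 in all ears.

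**Step 4: two alternative outcomes.**

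- *Residual ABG, continuous.* The mean given ABG ≥25 is μ + σφ(z)/(1 − Φ(z)), with z = (25 − μ)/σ. In the central case this is 12.1 + 10 × 0.1736/0.0985 = 29.7 dB and 17.1 + 10 × 0.2920/0.2148 = 30.7 dB. A 5 dB difference in all ears shrinks to about 1 dB. The outcome can be analysed, but it answers a narrower question.
- *ABG change from pre-operative.* Further assumptions: pre-operative SD 10, high-risk shift 3-5 dB before and 5-8 dB after surgery, pre/post correlation 0.2-0.5, post-operative SD 8-15. In all ears, high-risk ears improve 2 to 5 dB less. In ears with ABG ≥25 dB the difference in improvement ran from −2.6 to +2.4 dB and reversed sign in 11 of 18 combinations.

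**The case against.** The strongest reply is that Section 9.8 does not say which post-operative ABG it means, so a cut-off and audiogram that yield both classes could still be fixed in advance. This is right as far as it goes. A reader might infer that the data can contain no successes at all. The documents do not support that: zero is certain only for eligible subjects on the qualifying audiogram. Fixing the choice in advance would remove the risk of a data-driven cut-off. It would not remove the selection on early ABG.

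The analysis set might also be said to supply successes. Section 7.2.5 defines a screen failure as "An Enrolled subject that has been determined to not meet one or more eligibility criteria", and such subjects fall within the all-enrolled set. But records are screened before consent, so few are likely to fail criterion 5, and those who do are not a valid sample of successful ears.

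A reader might also infer from the unequal AC condition that the MERI association is biased in either direction. That is not shown. The illustration ignores the AC condition and shows weakening only, and criterion 6 (hearing aid recommended) may already limit ears with AC between 30 and 40 dB HL. Other bias cannot be excluded, and no more can be said.

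Finally, the analysis is exploratory, has no hypothesis and depends on available data, and Spearman in Section 9.8 already refers to post-operative outcomes generally. This stands and limits the weight of the point.

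**Conclusion.** The concern holds as a minor point. As written, Section 9.8 asks what predicts ABG-based success in a sample from which criterion 5 removes such success at the early assessment. On the qualifying audiogram there are 0 eligible successes at any cut-off up to 25 dB. From there to 30 dB the two classes are selected by different rules, and above 30 dB success means a smaller residual gap. Other audiograms avoid the empty class but not the selection. These statements follow from the criteria alone.

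That associations are probably weakened rests on the usual effect of restricting an outcome's range. The odds ratios above depend on assumed SDs, shifts and correlations, and the documents do not allow the true size to be estimated. A reader might infer wider damage, but the primary and secondary endpoints and the sample size do not rest on this model.

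**What to change.** In Section 9.8, replace the binary ABG-success regression with an analysis of residual post-operative ABG as a continuous outcome among ears with residual hearing loss, by MERI factor and by the two risk groups. Name the audiogram: the post-primary-tympanoplasty one. Keep Spearman, with its outcomes named.

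In Sections 6.3 and 9.8, state that tympanoplasty success rates, and MERI associations with success in all operated ears, cannot be estimated from this sample. Align the synopsis and Section 7.1, where the objective is repeated.

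Optionally, tabulate the MERI groups against the Appendix 1 surgical outcomes already collected where available. Report the time of assessment and note that these outcomes are seen in the same selected ears.

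Do not add ABG change from the pre-operative audiogram as a remedy. It contains the same truncated value and, under the assumptions above, often pointed the wrong way.

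The cost is a protocol amendment with ethics committee notification (Section 18), for exploratory wording only, and a narrower conclusion. The remaining associations would still be range-restricted. No new data are needed.
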